3.3. Protocol Deviation Subjects Handling

A listing of protocol deviations will be provided. Before database lock, the statistical team will programmatically check against the pre-specified criteria provided in a separate document, ie, Protocol Deviation Checklist, and produce a list of protocol deviations. The data review team will review the outputs and the protocol deviation tracker obtained during the study conduct, then determine the major/minor category for each deviation. If any data points or subjects are excluded from the analysis, they will be documented in the data review meeting minutes and also be presented in a data listing.

3.4. Reporting Precision

Summary statistics will be presented to the following degree of precision, unless otherwise specified:

Statistics	Degree of Precision
Mean, Geometric Mean, Median, Quartiles, Confidence Limit Boundaries	One (1) decimal place more than the raw data
Standard Deviation, Standard Error	Two (2) decimal places more than the raw data
Minimum, Maximum	The same as the raw data
Percentage	One (1) decimal place. A percentage of 100% will be reported as 100.0. Percentages of zero will be reported as 0.0.

Up to 3 decimal places will be presented. Fractional numeric values will be presented with a zero to the left of the decimal point (for example, 0.12 – 0.30).

4. SUBJECT DISPOSITION

The number of subjects included in each study population will be summarized. The number and percentage of subjects completed and discontinued will be presented by observation and treatment phase. Reasons for discontinuation as recorded on the eCRF will be summarized (number and percentage) and listed for all subjects.

5. DEMOGRAPHICS AND OTHER BASELINE CHARACTERISTICS

Demographic and baseline characteristics, including age, age group, race, and some other baseline values will be summarized for the Safety population and the Effectiveness population using appropriate descriptive statistics. Demographic and baseline characteristics will also be listed.

6. EFFECTIVENESS ANALYSES

6.1. Cellulite assessments

- PR-PCSS: 5-level ratings ranging from 0 (none) to 4 (severe). It will be assessed at Screening B, Days 22, Day 43, Day 71 and observational visits Day 90, Day 180, Day 270, Day 360 and Long-term Durability Visits, ie, Day 450, Day 540, Day 630, and Day 720.
- CR-PCSS: 5-level ratings ranging from 0 (none) to 4 (severe). It will be assessed at Screening B, Days 22, Day 43, Day 71 and observational visits Day 90, Day 180, Day 270, Day 360 and Long-term Durability Visits, ie, Day 450, Day 540, Day 630, and Day 720.
- Investigator rating of cellulite severity using the total scores from the Hexsel CSS scale: scores can range from 0 to 15. It will be assessed at Screening B, Day 71, Day 360 and Long-term Durability Visits.
- I-GAIS: 7-level ratings ranging from 3 (very much improved) to -3 (very much worse). This will be assessed at Day 71 and Day 360.
- S-GAIS: 7-level ratings ranging from 3 (very much improved) to -3 (very much worse). This will be assessed at Day 71 and Day 360.
- Subject satisfaction with cellulite treatment assessment: 5-level ratings ranging from +2 (very much satisfied) to -2 (very much dissatisfied). This will be assessed at Day 71 and Day 360.

All cellulite assessments will be done by treated quadrant and overall. For initial treatment subjects who have 2 quadrants treated, each quadrant will be evaluated separately. In the observation phase, those assessments will be also done corresponding to the treated quadrant.

6.2. Effectiveness Analysis

6.2.1. Composite Endpoints

The composite endpoints for cellulite severity are the proportions of composite responders defined as subjects with an improvement in severity from baseline of at least 2 (or 1) levels of severity in the CR-PCSS and an improvement in severity from baseline of at least 2 (or 1) levels of severity in the PR-PCSS.

These endpoints will be summarized by treated quadrant and overall (buttocks and thighs) and by study day using appropriate descriptive statistics.

6.2.2. Other Cellulite Assessment Endpoints

Other endpoints for treated quadrants in study EN3835-202 include:

- Change from baseline for PR-PCSS
- Proportion at each level of improvement in the PR-PCSS:
 - Proportion of patient responders defined as subjects with an improvement in severity from baseline of at least 2 levels on the PR-PCSS
 - Proportion of patient responders defined as subjects with an improvement in severity from baseline of at least 1 level on the PR-PCSS
- Change from baseline for CR-PCSS
- Proportion at each level of improvement in the CR-PCSS:
 - Proportion of Investigator responders defined as subjects with an improvement in severity from baseline of at least 2 levels on the CR-PCSS (Investigator rated)
 - Proportion of Investigator responders defined as subjects with an improvement in severity from baseline of at least 1 level on the CR-PCSS (Investigator rated)
- Proportion of responders at each level of the I-GAIS:
 - Proportion of subjects at each level of the I-GAIS ranging from 3 (very much improved) to -3 (very much worse). It will be assessed at Day 71 and Day 360.
- Proportion of responders at each level of the S-GAIS:
 - Proportion of subjects at each level of the S-GAIS ranging from 3 (very much improved) to -3 (very much worse). It will be assessed at Day 71 and Day 360.
- Proportion of responders at each level of the subject satisfaction with cellulite treatment
- Change in the Hexsel CSS total score from screening visit

All endpoints will be summarized by treated region (buttock or thigh) and overall and by study day using appropriate descriptive statistics, unless specified otherwise (eg, by treatment course).

6.2.3. Observation Endpoints

Observational endpoints for treated quadrant in study EN3835-201 include:

- Change from baseline for PR-PCSS
- Proportions of composite responders defined as subjects with an improvement in severity from baseline of at least 2 (or 1) levels of severity in the CR-PCSS and an improvement in severity from baseline of at least 2 (or 1) levels of severity in the PR-PCSS

- Proportion at each level of improvement in the PR-PCSS:
 - Proportion of patient responders defined as subjects with an improvement in severity from baseline of at least 2 levels on the PR-PCSS
 - Proportion of patient responders defined as subjects with an improvement in severity from baseline of at least 1 level on the PR-PCSS
- Change from baseline for CR-PCSS
- Proportion at each level of improvement in the CR-PCSS:
 - Proportion of Investigator responders defined as subjects with an improvement in severity from baseline of at least 2 levels on the CR-PCSS (Investigator rated)
 - Proportion of Investigator responders defined as subjects with an improvement in severity from baseline of at least 1 level on the CR-PCSS (Investigator rated)
- Proportion of responders at each level of the subject satisfaction at Day 360
- Hexsel CSS total score changed from the study EN3835-201 baseline at Day 71 of study EN3835-201 and Day 360 or Day 360 Beyond long-term durability visits.

These endpoints will be summarized by treatment groups assigned in study EN3835-201 and treated region (buttock or thigh) and overall and by study day using appropriate descriptive statistics.

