12.1.3.1. Three-Month Assessments

Subjects will return within 20 days (± 4 days) of completion of the double-blind study for the first of 4 safety and cellulite severity evaluation visits. Assessments to be completed at these visits are detailed in Table 2. Subjects are to return at 3-month intervals until they have completed 12 months from Day 1 of the double-blind study. At these visits, the quadrant previously treated with EN3835 in the EN3835-201 study or quadrants treated with EN3835 in the open-label study

will be evaluated. If the quadrant treated in study EN3835-201 is retreated in the open-label study, the 3-month assessments will reset to treatment visit 1/Day 1 of the open-label treatment and the study visits will continue as described in [Table 3](#) followed by 3-month assessments as described in [Table 2](#). If a different quadrant is treated in the open-label study, the 3-month assessments of both the quadrant treated in the double-blind study (EN3835-201) and the quadrant treated in the open-label study will continue.

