13.1.1.3. Subject Satisfaction with Cellulite Treatment Assessment

For observation-only subjects (not receiving EN3835) the subjects will assess their satisfaction with cellulite treatment at the 12 month or end of study visit by being instructed to answer the following question: *Today, how satisfied are you with the results of the cellulite treatment you received on the specific area or areas on your buttocks or thighs that were treated?* Subjects will circle the rating in the below table that best represents their answer.

For subjects who have elected to receive EN3835 either through re-treatment or re-dosing, the subject satisfaction with the cellulite treatment (Table 7) will be done at the treatment course Day 71 and the month 12 visit or end of study visit. Subjects will be instructed to answer the following question: *Today, how satisfied are you with the results of the cellulite treatment you received on the specific area or areas on your buttocks or thighs that were treated?* Subjects will circle the rating below that best represents their answer.

Table 7: Subject Satisfaction with Cellulite Treatment Assessment

Rating	Description
+2	I am very satisfied with the cellulite treatment on my buttocks or thighs.
+1	I am satisfied with the cellulite treatment on my buttocks or thighs.
0	I am neither dissatisfied nor satisfied with the cellulite treatment on my buttocks or thighs.
-1	I am dissatisfied with the cellulite treatment on my buttocks or thighs.
-2	I am very dissatisfied with the cellulite treatment on my buttocks or thighs.

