- Observation phase: Observation phase is defined as the time period from Screening A to the first treatment date of the same quadrant in study EN3835-202 or the end of study EN3835-202 if there is no treatment received for the same quadrant in study EN3835-202. Observation phase is defined within each treated quadrant, unless the summary is for subject level only and cannot be differentiated by the treated quadrant, ie, disposition, adverse event (AE). For subject level summaries, observation phase is defined as the time period from Screening A to the first treatment date in study EN3835-202 or the end of study EN3835-202 if there is no treatment received in study EN3835-202.
- Treatment phase: Treatment phase is defined as the time period from the first treatment date of certain quadrant in study EN3835-202 to the end of study EN3835-202. Treatment phase is defined within each treated quadrant, unless the summary is for subject level only and cannot be differentiated by the treated quadrant, ie, disposition, AE. For subject level summaries, treatment phase is defined as the time period from the first treatment date to the end of study EN3835-202.

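### Day 360 satisfaction is reported for the quadrant treated in study 201, but the question covers every treated area, so open-label EN3835 given in another quadrant can enter the 201 columns

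*Combined protocol and SAP*

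**What the plan says.** Protocol 13.1.1.3 puts one question to the woman about her treated areas: "how satisfied are you with the results of the cellulite treatment you received on the specific area or areas on your buttocks or thighs". It names no quadrant and no study. The answer options are equally general, for example "I am very satisfied with the cellulite treatment on my buttocks or thighs". The wording is the same in all three protocol versions in the file.

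SAP 6.2.3 lists "Proportion of responders at each level of the subject satisfaction at Day 360" and summarises it by 201 treatment group, by region (buttock or thigh) and overall. The lead-in to that list of endpoints is "Observational endpoints for treated quadrant in study EN3835-201 include". SAP 6.1 has satisfaction on its list of cellulite assessments and states: "All cellulite assessments will be done by treated quadrant and overall".

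SAP 2 sets the population and the cut-off. The Observation population is everyone who rolled over from 201. The phase rule reads: "Observation phase is defined within each treated quadrant, unless the summary is for subject level only and cannot be differentiated by the treated quadrant". At quadrant level the phase runs until that same quadrant is treated in 202, and otherwise to the end of the study. At subject level it stops at the first 202 treatment of any quadrant. The instances given for the subject-level rule are disposition and adverse events.

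**The concern.** The rating is a judgement on all the treatment a woman has had, yet it is filed as an outcome of one quadrant and one 201 arm. If she has EN3835 injected elsewhere in 202 before her 201 Day 360 visit, her answer reflects that course too, and nothing in the table shows it. The region split suffers as well: an answer covering a 201 buttock and a 202 thigh would be reported under buttock.

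Long-term subject satisfaction is a named secondary objective (protocol 9.2, SAP 1.3.2). SAP 6.2.3 does not carry over the Day 360 I-GAIS and S-GAIS endpoints that protocol 17.5.2 lists, so satisfaction is the only global rating by the subject left in the 201-arm observation tables. CR-PCSS, PR-PCSS and Hexsel CSS are scored quadrant by quadrant and do not have this problem.

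The protocol kept these women apart. Its Observational population (17.2.1) was limited to 201-active women with no treatment in 202, and re-dosed women had their own cohort (17.2). SAP 9 replaces both and does not address the satisfaction item.

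**Working it through.** **The plan's own figures.** The documents give no satisfaction rate, test, effect size or power for this endpoint, so there is none to reproduce. The enrolment figure in protocol 17.1 does reproduce (0.95 × 350 = 332.5, rounded up to 333), but the point does not depend on it.

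**Step 1: who is in the 201 Day 360 satisfaction table.** This applies the quadrant-level phase rule of SAP 2, the options in SAP 1.1 and protocol 12.1.4, and the note in SAP 1.2 that open-label treatment runs alongside the observation visits.

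| 201 arm | 202 treatment before 201 Day 360 | In the 201 table at Day 360? | What the answer reflects |
|---|---|---|---|
| Active | none | yes | 201 course |
| Active | same quadrant | no, phase has ended | – |
| Active | another quadrant | yes | 201 course and open-label course |
| Placebo | none | yes | 201 placebo |
| Placebo | same quadrant | no, phase has ended | – |
| Placebo | another quadrant | unclear (step 2) | placebo and open-label EN3835 |

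The third row is a foreseen case. Footnote f to SAP Table 2, attached to the Day 360 visit, deals with women who had active drug in 201 and a different quadrant treated in 202.

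**Step 2: the placebo row.**
- For a retained 201-based visit: protocol 12.1.3.1 has a continuation rule beginning "If a different quadrant is treated in the open-label study, the 3-month assessments of both the quadrant treated in the double-blind study". SAP 1.1 includes double-blind quadrants in the follow-up when the quadrants differ. Footnote b to SAP Table 2 counts visits from 201 Day 1.
- Against: SAP 1.1 also counts follow-up from first exposure to EN3835, which for a placebo woman is her open-label Day 1. Protocol 12.1.3.1 says the quadrants evaluated are those that received EN3835, and a placebo quadrant did not. Footnote c to SAP Table 2 has the treated quadrant photographed in women treated open-label.

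The text does not settle it.

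**Step 3: how far the figures could move.** Let f be the share of an arm treated in another quadrant before Day 360. Then

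observed share satisfied = (1 − f) × s(201 treatment only) + f × s(after open-label treatment elsewhere).

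All rates are assumptions: 50% satisfied after 201 active only, 20% after 201 placebo only, 60% after open-label EN3835 elsewhere in either arm. The difference without carry-over is 50 − 20 = 30 points.

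| f active | f placebo | Active column | Placebo column | Difference |
|---|---|---|---|---|
| 0.2 | 0.2 | 0.8×50 + 0.2×60 = 52% | 0.8×20 + 0.2×60 = 28% | 24 |
| 0.4 | 0.4 | 0.6×50 + 0.4×60 = 54% | 0.6×20 + 0.4×60 = 36% | 18 |
| 0.6 | 0.6 | 0.4×50 + 0.6×60 = 56% | 0.4×20 + 0.6×60 = 44% | 12 |
| 0.2 | 0.4 | 52% | 36% | 16 |
| 0 | 0.6 | 50% | 44% | 6 |
| 0.4 | 0 | 54% | 20% | 34 |
| 0.6 | 0 | 56% | 20% | 36 |

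The last two rows are the case in which placebo women do not keep a 201-based visit; the difference then widens. If satisfaction after the open-label course is set at 50%, the same as after 201 active, the active column stays at 50% whatever the share, and only the placebo column can move (26%, 32% and 38% at f = 0.2, 0.4 and 0.6). Even the direction therefore depends on quantities that the documents do not give.

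**The case against.** The best defence is that SAP 2 already solves this. Its subject-level cut-off is for summaries that cannot be separated by quadrant, which describes satisfaction well, and the two instances given can hardly be a full list, since vital signs and laboratory values are not quadrant-specific either. Against that, the instances are introduced by ie, and SAP 6.1 and 6.2.3 put satisfaction at quadrant level. Two programmers could reasonably build two different tables, so the wording needs settling on either reading.

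Second, the item may be administered per quadrant. Protocol 12.1.4.4 lists it among assessments of the selected quadrant made from the photograph, the SAP schedule footnotes tie it to images of treated quadrants, and SAP 6.1 has two treated quadrants evaluated separately. The case report form is not shown, so a single answer per woman is an inference. But a photograph does not change the question she reads, which asks about every treated area.

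Third, the endpoint is descriptive: no arm contrast or test is specified, and the objective concerns long-term response to EN3835. That stands, and it limits the harm to misattributed proportions.

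Fourth, the protocol version containing the SAP's visits beyond Day 360 is not in the file, so the final wording of the question could differ. That also stands as a caveat.

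A reader might infer that one answer is counted for both the 201 and the 202 quadrant. The documents do not support this as a rule. The 201 visits count from 201 Day 1 and the open-label quadrant's follow-up from open-label Day 1, so the two Day 360 visits fall on different dates. They could coincide only at a shared visit such as end of study or early termination.

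**Conclusion.** The point holds for the 201-active column: a woman re-dosed in another quadrant before her 201 Day 360 visit stays in the table with an answer that also reflects open-label EN3835. For the 201-placebo column the same carry-over is possible but not established, because the visit rules conflict.

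The size is unknown. It depends on the share treated elsewhere by Day 360 and on satisfaction afterwards, and the documents give neither, nor the date of unblinding. The 6-to-36-point range illustrates sensitivity on assumed rates and is not an estimate. Because the summary is descriptive, neither type I error nor power is affected.

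A reader might infer that the arm difference could reverse. The documents do not support that. If satisfaction after one EN3835 course is the same whichever study gave it, complete carry-over in the placebo arm only brings the columns level (50% against 50% in the second set of rates). Going further would need higher satisfaction after the open-label course than after the 201 course, and nothing in the documents suggests it.

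The correction is cheap and changes reported proportions for a named secondary objective, so it should be made.

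**What to change.** In SAP 2 and 6.2.3, name subject satisfaction as a subject-level summary, so that the existing subject-level observation cut-off (first 202 treatment of any quadrant) applies, and except it from the by-quadrant rule in SAP 6.1. Then:

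1. Show the 201 Day 360 satisfaction table for women with no 202 injection before the rating. These women have one treated quadrant, so the region split still works.
2. Beside it, show women already treated in 202 at the time of the rating, by number of EN3835 courses received (201 plus 202).
3. State whether a 201-placebo woman treated in another quadrant keeps her 201-based Day 360 visit.

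The work is SAP wording and one filter on the study drug administration record. The costs are smaller columns, no clean region split for the second group, and selection. Declining further treatment is a woman's own choice made after unblinding, and treatment also depends on eligibility, so those who remain untreated are not a random part of either arm. That is why the two groups belong side by side, with a note that the 201-arm columns are not a randomised comparison.

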1.2. Schedule of Study Assessments

[Table 2](#) lists the schedule of observation assessments, [Table 3](#) lists the schedule of treatment session assessments, [Table 4](#) lists the schedule of long-term durability assessments.

The schedule of observation assessments is applicable for both observation only and treated subjects in current study. For example, if subjects received treatments (ie, re-treatment, re-dosing, or a first treatment) in current study may be scheduled for observation assessments up to maximum of 1 year for each treated quadrant.

NOTE: Observation visits ([Table 2](#)) in the open-label extension study begin after completion of double-blind study (Day 71). Treatment sessions ([Table 3](#)), if elected, will begin after study drug blind is broken in study EN3835-201 while observation visits continue concurrently. Durability visits ([Table 4](#)) are for the subjects who received active treatment in EN3835-201 and scored an improvement of at least 1 level on both the CR-PCSS and the PR-PCSS at the same visit on or before Day 71 in the double-blind study EN3835-201.

Table 2: Schedule of Observation Assessments

Procedures	Screening A ^a (≥Day 71 Visit of Double-blind Study)	Visit 1 Day 90 ^b (±7 days)	Visit 2 Day 180 ^b (±7 days)	Visit 3 Day 270 ^b (±7 days)	Visit 4 End of Study/ Early Termination Day 360 ^{b,f} (±7 days)
Informed Consent	X				
Inclusion/Exclusion	X				
Digital photography		X ^c	X ^c	X ^c	X ^c
Prior/Concomitant Medications/Procedures	X	X	X	X	X
Body weight		X	X	X	X
Vital signs		X	X	X	X
Collection of samples:					
• Clinical laboratory					X
• Anti-AUX-I/anti-AUX-II antibody level					X
Subject cellulite assessments:					
• Patient Reported Photonumeric Cellulite Severity Scale (PR-PCSS)		X ^{d,e}	X ^{d,e}	X ^{d,e}	X ^{d,e}
• Subject Global Aesthetic Improvement (S-GAIS)					X ^{d,e}
• Subject satisfaction with cellulite treatment assessment					X ^{d,e}
Investigator cellulite assessments:					
• Clinician Reported Photonumeric Cellulite Severity Scale (CR-PCSS)		X ^e	X ^e	X ^e	X ^e
• Hexsel Cellulite Severity Scale (CSS)					X ^e
• Investigator Global Aesthetic Improvement (I-GAIS)					X ^e
Injection site reactions/local tolerability in assigned quadrant from EN3835-201 study		X	X	X	X
Adverse events		Monitored Throughout Study			

^a Informed consent for open-label observation assessments and optional treatment election.

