2. ANALYSIS POPULATIONS AND PHASES

The following populations will be considered in the statistical analysis of the study:

- Observation Population: The Observation population includes all subjects rolled over from study EN3835-201. The cellulite assessment evaluations and safety analyses on data collected during observation phase will be performed using this population.
- Safety Population: The Safety population will include all subjects who receive at least 1 dose of EN3835 in the current study. All safety analyses for the treatment phase will be performed using this population. For by region summaries, safety population is considered within each treatment course.
- Effectiveness Population: The Effectiveness population includes all safety subjects who have a baseline and at least 1 post-baseline assessment on both the CR-PCSS and PR-PCSS on the quadrant selected for treatment in the current study. All analysis of effectiveness for the treatment phase will be based on this population. For by region summaries, effectiveness population is considered within each treatment course.
- Durability Population: This population is defined as all active responders who have both CR-PCSS and PR-PCSS at 180 days or above. The active responders are subjects treated with EN3835 with improvements of at least 1 level on each

scale (CR-PCSS and PR-PCSS) at Day 71 visit compared to the baseline. Analysis of durability of treatment effect will be performed using this population.

- Durability Population for Double-blind Treated Subjects: This population is defined as all subjects in the durability population who showed an improvement of at least 1 level on each scale (CR-PCSS and PR-PCSS) at Day 71 visit compared to the baseline for the quadrant treated with EN3835 in double-blind study EN3835-201.
- Durability Population for Open-label Treated Subjects: This population is defined as all subjects in the durability population who showed an improvement of at least 1 level on each scale (CR-PCSS and PR-PCSS) at Day 71 visit compared to the baseline for the quadrant treated with EN3835 in the open-label study EN3835-202 study, who did not have the same quadrant treated with EN3835 in double-blind study EN3835-201. For by region summaries, this population is considered within each treatment course.

The following 2 phases will be summarized in the statistical analysis of the study:

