9. CHANGES TO PLANNED ANALYSES

The EN3835-202 protocol [Section 17.2] defines the 4 different cohorts and states all efficacy and safety analyses will be done within the classified cohort. In this statistical analysis plan, the efficacy and safety analyses are summarized by different phases (observation phase, treatment phase, long-term durability visits) and populations (observation population, safety population, effectiveness population, and durability population) instead.

The EN3835-202 protocol [Section 17.2.1] defines the observational population as including all subjects rolled over from the EN3835-201 study who do not receive any treatment in the current study. This population is renamed to “Observation Population” for this document, as described in section 2. It is defined as: The observation population includes all subjects rolled over from the EN3835-201 study. The cellulite assessment evaluations and safety analyses for the data collected from Screening A to Day 360 will be based on this population. This change will allow the data observed during observation phase to be summarized under this new population.

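### In SAP 6.2.3 the by-arm Hexsel summary changes after Day 360 from all EN3835-201 active-arm women still in observation to early responders only, with no placebo data

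*Combined protocol and SAP*

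**What the plan says.** Among the endpoints for the quadrant treated in EN3835-201, SAP 6.2.3 lists change in Hexsel total score from the 201 baseline at Day 71 and then at "Day 360 or Day 360 Beyond long-term durability visits". One sentence sets the layout for the whole section: "These endpoints will be summarized by treatment groups assigned in study EN3835-201 and treated region (buttock or thigh) and overall and by study day". SAP 6.1 agrees on the timing of Hexsel: "It will be assessed at Screening B, Day 71, Day 360 and Long-term Durability Visits".

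Section 6.2.3 names no population. SAP section 2 supplies one for observation-phase data: "The Observation population includes all subjects rolled over from study EN3835-201". It also sets the window: "Observation phase is defined as the time period from Screening A to the first treatment date of the same quadrant in study EN3835-202", or to the end of the study if that quadrant is not treated again. SAP section 9 gives a different window. There, the cellulite evaluations "for the data collected from Screening A to Day 360 will be based on this population", and long-term durability visits are listed as a phase of their own.

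The note in SAP 1.2 says who attends after Day 360: "subjects who received active treatment in EN3835-201 and scored an improvement of at least 1 level on both the CR-PCSS and the PR-PCSS", both at one visit no later than Day 71 of 201. Table 4, footnote d, limits assessment at those visits to the quadrant given active drug in 201. SAP 1.1 otherwise caps follow-up at one year per treated quadrant. SAP 8.1 imputes CR-PCSS and PR-PCSS but not Hexsel.

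**The concern.** A table by arm and study day invites the reader to follow a column as the course of one group. Here the active-arm column has one membership up to Day 360 and a narrower one afterwards, chosen on early response. The difference between the Day 360 and Day 450 means then mixes real change with the departure of non-responders, and the table offers no way to separate them. There is no placebo value alongside to show that something other than treatment is moving the figure.

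Durability beyond 12 months is a secondary objective (SAP 1.3.2). SAP 6.3 does analyse durability in responder populations, but only for CR-PCSS and PR-PCSS. Section 6.2.3 is therefore the only place where Hexsel after Day 360 is summarised.

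**Working it through.** **Who is in the Hexsel column at each day, following SAP 6.2.3 with section 2**

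| Study day | Active-arm column | Placebo column |
|---|---|---|
| 71 | All rolled-over active-arm women | All rolled-over placebo women |
| 360 | Active-arm women whose 201 quadrant is still in observation | Placebo women whose 201 quadrant is still in observation |
| 450 to 720 | Active-arm women with early response on both scales | None |

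Nothing in 6.2.3, section 2 or section 9 restricts the Day 71 and Day 360 rows to the women seen later.

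**Scale of the arm.** Protocol 17.1 expects 95% of 350 women: 0.95 × 350 = 332.5, which rounds up to the planned 333. With the 1:1 allocation in 201 (protocol 8.3.1.4), about 166 are active-arm. SAP 1.7 says approximately 350 instead; that alters the counts below but not the shift.

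**Formula.** Let r be the responder share of the active-arm column at Day 360. Let C_R and C_N be the mean Hexsel changes at Day 360 in responders and non-responders, and hold every woman's score constant afterwards.

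- Mean at Day 360 = r × C_R + (1 - r) × C_N
- Mean at Day 450 onward = C_R
- Shift = (1 - r) × (C_R - C_N)

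Hexsel runs from 0 to 15 with higher scores worse, so improvement is a negative change. Writing g for the size of responders' advantage, the spurious extra improvement is (1 - r) × g.

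**Numbers.** Neither r nor g is in the documents. The values below are assumptions, and the counts ignore drop-out and re-treatment.

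| r | n at Day 360 | n at Day 450 | g = 1 | g = 2 | g = 3 |
|---|---|---|---|---|---|
| 0.3 | about 166 | 50 | 0.7 | 1.4 | 2.1 |
| 0.4 | about 166 | 67 | 0.6 | 1.2 | 1.8 |
| 0.5 | about 166 | 83 | 0.5 | 1.0 | 1.5 |
| 0.6 | about 166 | 100 | 0.4 | 0.8 | 1.2 |

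For example, take r = 0.5 with responders at -3 and non-responders at -1. The mean is 0.5 × (-3) + 0.5 × (-1) = -2.0 at Day 360 and -3.0 at Day 450, and no woman has changed.

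**Simulation check.** This used 400,000 women, a constant true change with assumed mean -2 and SD 2, and r = 0.5. The correlation is between Day 71 response and true Hexsel change.

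| Correlation | All active-arm, Day 360 | Responders, Day 450 | Same responders, Day 360 |
|---|---|---|---|
| 0 | -1.99 | -1.99 | -2.00 |
| 0.2 | -2.00 | -2.31 | -2.31 |
| 0.4 | -2.00 | -2.64 | -2.63 |
| 0.6 | -2.00 | -2.95 | -2.95 |

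The shift is zero when early response is unrelated to later Hexsel change and grows as they become related. Comparing the same women at both days removes it.

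**The case against.** The strongest reply is that the SAP already separates these data. Section 9 ends the Observation population's evaluations at Day 360, treats the durability visits as a separate phase, and lists a durability population. On that reading the mixed column is never built. This stands in part: what is shown is a conflict between section 9 on one side and 6.2.3 with the phase definition on the other. A reader might infer a settled plan to present a mixed-population trend, and the text does not go that far. But the Hexsel line in 6.2.3 explicitly passes Day 360, and section 9 does not say where those values go instead.

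A reader might also extend the point to CR-PCSS and PR-PCSS, since SAP 6.1 schedules both to Day 720. The documents do not support that as a finding. Section 6.1 is a schedule, only the Hexsel line in 6.2.3 names visits after Day 360, and 6.3 already analyses the two scales in responders. They are exposed only if their by-study-day summaries in 6.2.3 are run past Day 360.

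The size is open to challenge too. Besides r and g being assumed, g must be the gap at Day 360, which narrows if responders lose their response. Re-treatment of an active-treated quadrant requires scores at or above the 201 baseline (Table 3, footnote j) and ends that quadrant's observation phase. Some non-responders and relapsers may thus have left before Day 360, so an arm-wide r could overstate the shift.

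Three further points are fair. SAP 3.1 requires the observed count, so the fall in n would be visible. The summaries are descriptive, in a study whose primary objective is safety. The durability objectives in SAP 1.3.2 name CR-PCSS and PR-PCSS, not Hexsel. These limit the harm but leave the column inconsistent.

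Finally, some wording is looser than the SAP 1.2 rule. SAP 1.1 says assessments beyond Day 360 may extend to women who declined further treatment, and Table 2, footnote f, sends some active-arm women to Table 4 without stating a response condition. The protocol text supplied does not contain these visits, so it cannot settle the matter. Responders only remains the likelier reading. Neither sentence adds placebo-arm women.

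**Conclusion.** The point holds for Hexsel. Followed as written with section 2, SAP 6.2.3 gives an active-arm column that changes after Day 360 from all active-arm women still in observation to early responders, beside an empty placebo column. It also contradicts the Day 360 limit in section 9.

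A reader might conclude that the mean will certainly improve at Day 450. The documents do not establish that. A spurious extra improvement appears only if early responders still have the better Hexsel change at Day 360, which is plausible but not stated. The range of 0.4 to 2.1 points is illustrative, resting on r of 0.3 to 0.6 and g of 1 to 3, and may be too large if re-treatment has already removed poorer quadrants. Nor do the documents show that the table would be taken as two-year durability evidence, since 6.3 is the designated durability analysis. The correction is still worth making: it removes a foreseeable bias and an internal conflict at almost no cost.

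**What to change.** - End all by-arm Observation-population summaries in SAP 6.2.3 at Day 360. Align the Hexsel line and the observation-phase definition in section 2 with section 9.
- Report Hexsel at Days 450 to 720 only in a named, fixed responder set of women given active drug in 201. Show the same women's baseline, Day 71 and Day 360 values and the n at each day. Label the table as responders only, without a placebo comparator.
- State which responder definition that set uses. SAP 1.2 admits women to the visits on response on or before Day 71. The durability population in section 2 requires response at Day 71 and both scores at 180 days or later. A woman who responded at Day 43 but not at Day 71 could attend the visits yet fall outside that population.
- Align the looser wording in SAP 1.1 and Table 2, footnote f, with the chosen rule.

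The cost is SAP wording and one re-specified table. No new data are needed.
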